7.1.2.6.3 End of Treatment and Follow-up Tumor Imaging

In subjects who discontinue trial treatment, tumor imaging should be performed at the time of treatment discontinuation (± 4 week window). If a previous scan was obtained within 4 weeks prior to the date of discontinuation another scan at treatment discontinuation isn't mandatory. In subjects who discontinue trial treatment due to documented disease progression, this is the final required tumor imaging.

In subjects who discontinue trial treatment without documented disease progression, every effort should be made to continue monitoring their disease status by tumor imaging using the same imaging schedule the subject was on during treatment (e.g. every 9 weeks [63 days ± 7 days] from the date of allocation or every 12 weeks [84 days ± 7 days] from the date of allocation) until: 1) the start of new anti-cancer treatment, 2) disease progression, 3) death or 4) the end of the study, whichever occurs first.

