	
Subjects who discontinue after 35 infusions of pembrolizumab for reasons other than disease progression or intolerance, or who discontinue after attaining a complete response (and had at least 8 administrations of pembrolizumab and at least 2 treatments beyond initial CR) may be eligible for up to 17 additional infusions (approximately one year) after they have experienced radiographic disease progression.
 
After the end of treatment, each subject will be followed for the occurrence of adverse events as described under section 7.2 of the protocol. Subjects who discontinue for reasons other than disease progression will have post-treatment follow-up for disease status until disease progression is confirmed by the site, initiating a non-study cancer treatment, withdrawing consent, or becoming lost to follow-up. All subjects will be followed by telephone for overall survival until death, withdrawal of consent, or the end of the study.

--	--

A list of abbreviations used in this document can be found in Section 12.4.

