5.8 Subject Withdrawal/Discontinuation Criteria

5.8.1 Discontinuation of Treatment

Discontinuation of treatment does not represent withdrawal from the trial.

As certain data on clinical events beyond treatment discontinuation may be important to the study, they must be collected through the subject's last scheduled follow-up, even if the subject has discontinued treatment. Therefore, all subjects who discontinue trial treatment prior to completion of the treatment will still continue to participate in the trial as specified in Section 6.0 - Trial Flow Chart and Section 7.1.5.3 – Post Treatment.

Subjects may discontinue treatment at any time for any reason or be dropped from treatment at the discretion of the investigator should any untoward effect occur. In addition, a subject may be discontinued from treatment by the investigator or the Sponsor if treatment is inappropriate, the trial plan is violated, or for administrative and/or other safety reasons. Specific details regarding procedures to be performed at treatment discontinuation are provided in Section 7.1.4 – Other Procedures.

A subject must be discontinued from treatment but continue to be monitored in the trial for any of the following reasons:

- The subject or subject's legally acceptable representative requests to discontinue treatment.
- The subject has a medical condition or personal circumstance which, in the opinion of the investigator and/or sponsor, placed the subject at unnecessary risk from continued administration of study drug.
- The subject has a positive urine drug screen at any time during the course of the trial.
- Documented disease progression as assessed by the investigator using PCWG3-modified RECIST 1.1 guidelines (Section 7.1.2.6.1 – Initial Tumor Imaging). Two consecutive assessments are needed for disease progression. Clinical deterioration will not be considered progression.
- Unacceptable adverse experiences as described in Section 5.2.1.2 – Dose Modification (Escalation/Titration/Other) and Section 5.6.1 – Supportive Care Guidelines
- Intercurrent illness that prevents further administration of treatment
- Noncompliance with trial treatment or procedure requirements
- Administrative reasons

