7.1.2.6 Tumor Imaging and Assessment of Disease

The process for image collection and transmission to the central imaging vendor can be found in the Site Imaging Manual (SIM).

Tumor imaging should be acquired by CT (strongly preferred) and radionuclide bone scan. Magnetic resonance imaging should be used where CT is contraindicated or for imaging in the brain. The same imaging technique regarding modality and use of contrast should be used in a subject throughout the trial to optimize the visualization of existing and new tumor burden. Tumor imaging by both CT (or MRI) and radionuclide bone scan is required at every scheduled imaging time point.

All scheduled images for all subjects must be submitted to the central imaging vendor. Imaging obtained at unscheduled time points must also be sent to the central imaging vendor if the images support new or worsening metastatic disease based on site assessment.

Central review of baseline scans will be used to determine cohort assignment. Local review of imaging will be used for subject management. The central imaging vendor will receive radiologic images during the course of the study and will perform an analysis of response to treatment.

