##### Secondary

- **Duration of Response (DOR) – per RECIST 1.1 assessed by central imaging vendor**

For subjects who demonstrated CR or PR, DOR is defined as the time from first documented evidence of CR or PR until progressive disease (PD) assessed by central imaging using RECIST 1.1 or death due to any cause, whichever occurs first.

- **Duration of Response (DOR) – per PCWG3-modified RECIST 1.1 assessed by central imaging vendor**

For subjects who demonstrated CR or PR, DOR is defined as the time from first documented evidence of CR or PR until progressive disease (PD) assessed by central imaging where PD will be determined by radionuclide bone scan using RECIST 1.1/PCWG3 criteria and PD for all other tumors will be determined using RECIST 1.1 or death due to any cause, whichever occurs first.

- **Disease Control Rate (DCR) – per PCWG3-modified RECIST 1.1 assessed by central imaging vendor**

Proportion of subjects in the analysis population who have CR or PR or stable disease (SD) or Non-CR/Non-PD for at least 6 months, by central imaging vendor where PD in bone-only tumors will be determined by radionuclide bone scan using PCWG3 criteria and PD for all other tumors will be determined using RECIST 1.1.

- **PSA Response Rate**

Proportion of subjects in the analysis population who have PSA response defined as at least 50% ( $\geq 50\%$ ) decline from baseline measured twice at least 3 weeks apart, i.e. the number of subjects with PSA response divided by the total number of subjects with PSA measurement at baseline. Response must be confirmed by a second PSA value 3 or more weeks later.

- **Time to PSA Progression**

Time to PSA progression is defined as the time from first day of study treatment to the date of PSA progression. Subjects without PSA progression will be censored at the last PSA assessment date. For subjects who have a decline in PSA, the PSA progression date is defined as the date that an increase of 25% or more and an absolute increase of 2ng/mL or more from the nadir is documented.

For subjects who have no decline in PSA, the PSA progression date is defined as the date that an increase of 25% or more and an absolute increase of 2ng/mL or more, at least 12 weeks from the baseline is documented. If the PSA value at progression is less than the baseline, then PSA progression must be confirmed by a second value 3 or more weeks later.

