- **Radiographic progression-free survival (rPFS) – per PCWG3-modified RECIST 1.1 assessed by central imaging vendor**

Progression-free-survival (rPFS) is defined as the time from first day of study treatment to the documented disease progression by central imaging vendor where PD in bone-only tumors will be determined by radionuclide bone scan using PCWG3 criteria and PD for all other tumors will be determined using RECIST 1.1 or death due to any cause, whichever occurs first.

- **Overall Survival (OS)**

Overall survival (OS) is defined as the time from first day of study treatment to the time of death.

- **Duration of PSA response (Cohorts 4 and 5 only)**

Duration of PSA response is defined as the time from PSA response, when the PSA value first declines by at least 50% of the baseline (must be confirmed by a second value), to the date of PSA progression at which there is an increase of 25% or more from the nadir PSA, provided the absolute increase from the nadir PSA is at least 2ng/mL.

- **Time to initiation of cytotoxic chemotherapy (Cohorts 4 and 5 only)**

Time to initiation of cytotoxic chemotherapy is defined as the time from first day of study treatment to the time of initiation of cytotoxic chemotherapy for prostate cancer.

- **Time to new-anticancer therapy (Cohorts 4 and 5 only)**

Time to new-anticancer therapy is defined as the time from first day of study treatment to the time of new-anticancer therapy for prostate cancer

- **Time to first skeletal-related event (Cohorts 4 and 5 only)**

Time to initiation of first skeletal-related event is defined as the time from first day of study treatment to the first skeletal-related event, which is defined as radiation therapy or surgery to bone, pathologic bone fracture, spinal cord compression, or change or antineoplastic therapy to treat bone pain.

See [Section 3.6.1](#) for censoring rules.

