### 3.6 Statistical Methods

#### 3.6.1 Statistical Methods for Efficacy Analyses

For ORR, DCR and PSA response rate, the point estimate and 95% confidence interval will be provided using the exact binomial method proposed by Clopper and Pearson (1934) [3]. Subjects in the analysis population without response data will be counted as non-responders.

For rPFS, DOR, time to PSA progression, duration of PSA response, time to initiation of cytotoxic chemotherapy, time to new-anticancer therapy, time to first skeletal-related event, and OS, Kaplan-Meier (KM) curves and median estimates from the KM curves will be provided as appropriate.

Censoring rules for DOR are summarized in [Table 1](#).

Table 1 Censoring Rules for DOR

Situation	Date of Progression or Censoring	Outcome
No progression nor death, no new anti-cancer therapy initiated	Last adequate disease assessment	Censor (non-event)
No progression nor death, new anti-cancer therapy initiated	Last adequate disease assessment before new anti-cancer therapy initiated	Censor (non-event)
Death or progression immediately after $\geq 2$ consecutive missed disease assessments or after new anti-cancer therapy, if any	Earlier date of last adequate disease assessment prior to $\geq 2$ missed adequate disease assessments and new anti-cancer therapy, if any	Censor (non-event)
Death or progression after $\leq 1$ missed disease assessments and before new anti-cancer therapy, if any	PD or death	End of response (Event)
A missed disease assessment includes any assessment that is not obtained or is considered inadequate for evaluation of response.		

Censoring rules for rPFS are summarized in [Table 2](#).

Table 2 Censoring Rules for Analyses of rPFS

Situation	Rule
PD or death documented after $\leq 1$ missed disease assessment, and before new anti-cancer therapy, if any	Progressed at date of documented PD or death
PD or death documented immediately after $\geq 2$ consecutive missed disease assessments or after new anti-cancer therapy, if any	Censored at last disease assessment prior to the earlier date of $\geq 2$ consecutive missed disease assessment and new anti-cancer therapy, if any
No PD and no death; and new anticancer treatment is not initiated	Censored at last disease assessment
No PD and no death; new anticancer treatment is initiated	Censored at last disease assessment before new anticancer treatment

[Table 3](#) summarizes the key efficacy analyses.

Table 3 Analysis Strategy for Key Efficacy Variables

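### rPFS and DOR are read centrally but required imaging can end on the site's PD call; the resulting censoring is probably informative, likely raises both estimates modestly, and no supplementary analysis covers it

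*Protocol*

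**What the plan says.** **Who decides progression for the endpoint.** sSAP 3.4.1 defines rPFS as "time from first day of study treatment to the documented disease progression by central imaging vendor" or death. One DOR endpoint is the "time from first documented evidence of CR or PR until progressive disease (PD) assessed by central imaging using RECIST 1.1" or death; the other uses central PCWG3-modified RECIST 1.1.

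**Who decides when scans stop.** Protocol 7.1.2.6 says "Local review of imaging will be used for subject management". Under Protocol 5.8.1 treatment stops for "Documented disease progression as assessed by the investigator using PCWG3-modified RECIST 1.1 guidelines". The Trial Summary (1.0) ends disease follow-up at site confirmation: "post-treatment follow-up for disease status until disease progression is confirmed by the site". Protocol 7.1.2.6.3 then closes imaging: "In subjects who discontinue trial treatment due to documented disease progression, this is the final required tumor imaging". Table 5 of the Protocol likewise asks for no more scans once a repeat scan confirms PD. Neither document requires the central vendor to agree first.

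**The safeguard.** Protocol 7.1.2.6.2 has the site confirm soft-tissue PD at least 4 weeks later and bone PD at least 6 weeks later. If the repeat scan does not show PD, scheduled imaging resumes. All scheduled scans go to the central vendor, as do unscheduled scans that the site thinks show new or worsening disease (7.1.2.6). Clinically unstable subjects may stop at first site PD without a repeat scan (7.1.2.6.5).

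**The censoring.** sSAP 3.6.1, Tables 1 and 2, censor PD or death that comes straight after two or more consecutive missed assessments, or after new anti-cancer therapy. A subject with no PD or death who starts new therapy is "Censored at last disease assessment before new anticancer treatment" in the rPFS table. PD or death after at most one missed assessment and before new therapy remains an event. The note under Table 1 (DOR) reads "A missed disease assessment includes any assessment that is not obtained or is considered inadequate for evaluation of response". Table 2 (rPFS) has no such note.

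**The concern.** A subject whom the site calls progressed, but the central reader does not, leaves scheduled imaging. From then on he can have no central PD. A later death counts only if it comes soon enough and before new therapy. Otherwise he is censored at about the scan on which a physician judged him to be progressing. Kaplan-Meier treats him as having the same outlook as those who stay on study, which is doubtful.

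Reader variation is not the only source of discordance. The site applies PCWG3-modified criteria, while one DOR endpoint uses RECIST 1.1 alone, so a responder stopped for bone progression may have no event under that endpoint.

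The trial is single-arm estimation, so absolute rPFS and DOR figures are reported with no control arm to absorb a shared bias. No sensitivity analysis, concordance report or count of such subjects is planned.

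**Working it through.** The plan states no event count, assumed median or power for rPFS or DOR, so there is no figure of its own to reproduce. What follows is illustrative.

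**Inputs**
- Scans every 9 weeks through Week 54 (Protocol 7.1.2.6.2).
- Median time to site PD 4.1 months = 17.83 weeks; median survival 12.2 months = 53.05 weeks. Both are borrowed from the retrospective enzalutamide data in Protocol 4.2.1 and are assumptions here; exponential times.
- Discordance d = 10, 20, 30% of site PD calls, with central PD one 9-week scan later in those subjects. Assumed.
- The missed-scan note under Table 1 is assumed to apply to rPFS and to scans no longer required.

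**Step 1. Building blocks.** Chance of site PD per scan: p = 1 − 2^(−9/17.83) = 0.295, so q = 1 − p = 0.705. Alive at Week 27: 2^(−27/53.05) = 0.703.

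**Step 2. No confirmatory scan, every discordant subject censored at the site-PD scan.**
- As written: S(27) = [1 − (1 − d)p]³ × 0.703
- Imaging continued to central PD: S(27) = [q³ + d·q²·p] × 0.703, with q³ = 0.350 and q²p = 0.147

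| d | As written | Imaging continued | Excess |
|---|---|---|---|
| 10% | 27.8% | 25.6% | +2.2 |
| 20% | 31.3% | 26.7% | +4.7 |
| 30% | 35.1% | 27.7% | +7.4 |

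(Excesses are from unrounded values.) A simulation of 30,000 subjects per scenario gave 27.8 vs 25.6, 30.8 vs 26.3 and 34.5 vs 27.3, so about +2, +4.5 and +7.

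**Step 3. With a centrally read confirmatory scan at 6 weeks.** Assume 20% of discordant subjects are unstable and have no repeat scan, and that central progression falls evenly over the 9 weeks after site PD. The share still without central PD is u = 0.2 + 0.8 × (1 − 6/9) = 0.467. Subjects caught on the repeat scan have the same central PD date either way, so the excess is close to that of Step 2 at d × u = 4.7, 9.3 and 14.0%:
- 26.1 − 25.1 = +1.0
- 27.6 − 25.6 = +2.0
- 29.2 − 26.0 = +3.1 (unrounded values)

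Simulation with half starting new therapy gave about +1.0, +2.2 and +3.4. If confirmation waits for the next 9-week scan, it is about +0.5, +1.0 and +1.5.

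**Step 4. Deaths that still count.** The second missed scan falls about 18 weeks after the last one. Chance of dying within it: 1 − 2^(−18/53) = 21%. Simulation gave 21–23% of discordant subjects with no new therapy, 11% if half start it and 0% if all do.

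**Step 5. The median.** Alive at Week 18: 0.790. As-written S(18) = [1 − (1 − d)p]² × 0.790 = 42.6, 46.1 and 49.7%. Just before Week 18 it is at least 0.705 × 0.790 = 55.7%. The median stays at Week 18 in all three cases.

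**Step 6. Second simulation, differently built.** It used 200,000 subjects per scenario and put site PD one visit before central PD, with no confirmatory scan. With median central PD of 18 weeks, continued-imaging S(26) should be 0.5 × 2^(−26/53) = 35.6%; it gave about 35.5%. (Week 26 precedes the Week 27 scan, so its level is not comparable with Step 2.) With half starting new therapy, the sSAP rule gave 36.5, 37.5, 38.3 and 39.6% at 10, 20, 30 and 40% discordance. Only about half the nominally discordant subjects became so (at 20%: 8.9% censored + 1.1% dead as events = 10.0% of all). Over 36 scenarios the excess was +0.6 to +4.8 points at 26 weeks and +0.5 to +6.4 at 52 weeks; the largest median shift was 18 to 23 weeks. Where site PD was unrelated to later central PD, the shift was −0.1 to −0.3 points.

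**Step 7. Counting site PD as an event.** In the Step 2 model this gives q³ × 0.703 = 24.6%, below the continued-imaging values by 1.0, 2.0 and 3.1 points (unrounded values). The second simulation gave 34.5, 33.5 and 32.3% against about 35.5%: lower by 1.0, 2.0 and 3.2.

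**The case against.** The strongest answer is the confirmatory scan. For most subjects, discordance has to survive a second scan that the central reader also sees, and Step 3 shows that this roughly halves the effect. That stands. It does not remove the problem, because the subjects exempt from a repeat scan are the clinically unstable ones, in whom informative censoring is most plausible.

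The planned summaries are Kaplan-Meier curves and medians, a Week 27 rate is not named, and the median often does not move. That also stands, although the curve itself shifts. The endpoints are secondary, nothing is tested, and the sSAP describes its censoring rules as a company standard. These points limit the severity.

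A reader might infer that discordant subjects can hardly ever have an event, or that every later death is lost. Tables 1 and 2 do not say so: death or PD after at most one missed assessment and before new therapy is an event. A reader might also infer that the bias must always favour the drug. That needs site PD to predict later central PD or death, which is plausible but not shown; without that link the simulated shift was about zero. Finally, the missed-scan definition sits under the DOR table, so carrying it to rPFS is an interpretation.

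**Conclusion.** The gap is real. Central progression defines both endpoints, the site's call ends required imaging without central verification, and no planned analysis addresses the subjects caught between the two. The censoring is probably informative and likely biases rPFS and DOR upward, provided site PD predicts central PD or death.

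On the stated assumptions the Week 27 rPFS excess is roughly 1, 2 or 3 points at 10, 20 or 30% discordance with a centrally read confirmatory scan. About 2, 4.5 or 7 points is the upper end, reached only with no confirmatory scan, so it should not be read as the expected size under this protocol. The discordance rate is not in the documents. The effect on DOR was not computed. Primary ORR and OS are unaffected. This is a worthwhile, inexpensive improvement to secondary estimates and does not undermine the trial's main result.

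**What to change.** Add to sSAP 3.6.1 one pre-specified supplementary analysis of rPFS and DOR in which:
- site-assessed PD that ended imaging counts as an event at the site PD date when no central PD is recorded; and
- PD and deaths count regardless of missed scans or new anti-cancer therapy.

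Present it beside the main estimate, labelled a conservative lower bound, since Step 7 shows that it errs downward by about as much as the main analysis may err upward. Report how many subjects were censored after site PD without central PD. State under Table 2 whether the missed-assessment note applies to rPFS and to scans no longer required.

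The cost is some extra programming on data the protocol already calls for: site assessments, subsequent therapy and survival status. No scan or treatment rule changes. The downside is a second, less favourable figure that may understate rPFS and DOR.

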7.1.2.6.4 Second Course (Retreatment) Tumor Imaging

A scan must be performed within 28 days prior to restarting treatment with pembrolizumab. Local reading (investigator assessment with site radiology reading) will be used to determine eligibility. Imaging should be submitted to the central imaging vendor for retrospective review.

On study imaging assessments should be performed every 9 weeks (63 days \pm 7 days) after the restart of treatment or more frequently if clinically indicated.

If tumor imaging shows initial PD (Section 7.1.2.6.), tumor assessment should be repeated \geq 4 weeks later in order to confirm PD with the option of continuing treatment while awaiting radiologic confirmation of progression. Subjects who obtain a confirmation scan do not need to undergo scheduled tumor imaging if it is $<$ 4 weeks later and may wait until the next scheduled imaging time point if clinically stable.

Per PCWG3, if radionuclide bone scan shows progression in bone, a radionuclide bone scan should be repeated \geq 6 weeks later in order to confirm PD with the option of continuing treatment while awaiting radiologic confirmation of progression. Subjects who obtain a confirmation bone scan do not need to undergo the next scheduled bone scan and may wait until the next scheduled time point if clinically stable.

Imaging should continue to be performed until disease progression, the start of new anti-cancer treatment, withdrawal of consent, death, or notification by the Sponsor, whichever occurs first.

In subjects who discontinue trial treatment, tumor imaging should be performed at the time of treatment discontinuation (\pm 4 week window). If a previous scan was obtained within 4 weeks prior to the date of discontinuation, then a scan at treatment discontinuation isn't mandatory.

In subjects who discontinue trial treatment due to documented disease progression, this is the final required tumor imaging. In subjects who discontinue trial treatment without documented disease progression, every effort should be made to continue monitoring their disease status by radiologic imaging using the same schedule the subject was on during treatment (e.g. every 9 weeks from the date of allocation or every 12 weeks [63 days \pm 7 days] from the date of allocation) until: 1) the start of new anti-cancer treatment, 2) disease progression, 3) death or 4) the end of the study, whichever occurs first.

